5. ANALYSIS POPULATIONS

5.1 COHORT 2

5.1.1 Enrolled Population

The Enrolled population includes all subjects who gave informed consent/assent.

5.1.2 Intention-to-Treat (Randomized) Population

The ITT (or Randomized) population includes all subjects randomized to receive study treatment.

5.1.3 Modified Intention-to-Treat (mITT) Population

The mITT Population is defined as all randomized subjects who receive at least one dose of ZX008 or placebo and for whom at least one week of diary data are available. Subjects will be analyzed according to the treatment group to which they were randomized. The primary comparison of ZX008 0.5 mg/kg/day to placebo, as well as key secondary analyses, will be performed on the mITT Population.

5.1.4 Per Protocol (PP) Population

The per protocol population includes all randomized subjects who receive at least one dose of ZX008 or placebo, complete at least 4 weeks of the Maintenance Period, and have no important protocol deviations that would have a significant impact on clinical outcome. Subjects will be analyzed according to the treatment group to which they were randomized. Protocol deviations will be reviewed and the list of deviations warranting exclusion from the PP Population will be finalized prior to study unblinding.

For cohort 2, the primary and key secondary efficacy analyses will be repeated on the PP Population.

5.1.5 Safety Population

All safety analyses will be performed on the SAF Population defined as all randomized subjects who receive at least one dose of ZX008 or placebo. Subjects will be analyzed according to the treatment group to which they were randomized.

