10. STATISTICS

10.1 DETERMINATION OF SAMPLE SIZE

No formal hypothesis tests are planned for the PK endpoints studied in Cohort 1. Thus, the sample size for Cohort 1 is based on practical considerations including the expected availability of appropriate subjects. The PK data from Cohort 1 will be used in combination with PBPK models that are being developed using robust data from adults and from existing PBPK models for the concomitant medications. In this way, the data from ZX008-1504 will be leveraged with existing PK information on fenfluramine, stiripentol, clobazam and valproate acid to confirm the expectations derived from the mechanism-based PBPK models. Analysis of the data in this way allows for the confirmation of the appropriateness of the extension of the PBPK model from adults to children and a robust assessment of the potential for a drug-drug interaction between ZX008 and stiripentol while limiting exposure to a smaller number of patients. The 18-20 subjects targeted for the PK phase of the study is expected to be sufficient to allow for the extension of the PK information gained in the ongoing PK study in adults and existing PBPK models to pediatric patients with Dravet syndrome.

The sample size for Cohort 2 is based on results from Study 1, the randomized, placebo-controlled study in subjects with Dravet syndrome sponsored by Zogenix (Lagae 2017). The standard deviation (SD) of the percentage change in seizure frequency from baseline to the end of study (Day 99) was 50% for the 0.8 mg/kg/day group and 69% for the 0.2 mg/kg/day. For the sample size calculation for Cohort 2, the SD is assumed to be intermediate between the SDs observed in the high and low dose groups in Study 1. Assuming an SD of 58, and using a two-sided test at the $\alpha=0.05$ significance level, a sample size of 45 subjects per treatment group affords 90% power to detect a difference in mean change in seizure frequency from baseline of 40 percentage points. Thus, the total sample size for Cohort 2 is planned to be approximately 90 subjects (45 per arm).

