10.2 ANALYSIS POPULATIONS (COHORT 2)

10.2.1 Safety (SAF) Population

All safety analyses will be performed on the Safety (SAF) Population defined as all randomized subjects who receive at least one dose of ZX008 or placebo. Subjects will be analyzed according to the treatment actually received.

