3.2 COHORT 2 STUDY TREATMENT

The study period of cohort 2 subjects comprises a Baseline period (6 weeks), a T+M period (15 weeks: (21 days for dose titration + 12 weeks maintenance), a Taper period or transition period, and a Post Dosing visit after study completion or early termination.

Upon completion of the Baseline Period, subjects who qualify for the study will be randomized (1:1) in a double-blind manner to receive ZX008 (0.5 mg/kg/day, 20 mg/day maximum) or placebo. Randomization will be stratified by age group (<6 years, \geq 6 years) to ensure balance across treatment arms, and initially it was hoped that at least 40% of subjects will be in each age group. The actual % of subjects in each stratum may be different from this goal. Subjects will be assigned a randomization number by the IVR/IWR system upon confirmation that the subject qualifies for enrollment in the Titration Period. All subjects will be titrated to their randomized dose during the Titration Period. Titration will occur in 3 steps starting with a 0.2 mg/kg/day dose of ZX008 (or placebo equivalent) on Study Days 1-7, increased to a dose of 0.4 mg/kg/day on Study Day 8-14, and then increased to a dose of 0.5 mg/kg/day on Study Days 15-21; the maximum daily dose at any point is 20 mg/day. The duration of the titration period will be 21 days.

There will be cardiac safety follow-up of 3 to 24 months after study drug discontinuation for early termination or for subjects who complete the study but do not enroll in the open-label extension study. These results will be presented elsewhere.

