6.4 SAFETY ANALYSES

All safety analyses will be performed for the Safety population (SAF) and will be reported by treatment group, and overall.

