6.9 CHANGES TO METHODS PLANNED IN THE PROTOCOL

- Protocol states that safety data will be summarized separately for the titration and maintenance periods as well as for the combined T+M period. Instead safety will be summarized only for the combined T+M..
- Protocol states that subjects in the safety population will be summarized by the treatment actually received. However, safety data will be presented by randomized treatment group except where noted otherwise.
- Protocol states that a sensitivity analysis for the primary efficacy endpoint will be conducted by adding a factor indicating whether a subject had a change in prescribed

dose or type of concomitant AED medication during the T+M Period, however this is not planned to be conducted.

- The protocol stated that the longest interval between convulsive seizures will be analyzed using a log-rank test. Instead groups will be compared with a Wilcoxon test.
- Responder analyses – The protocol included a $\geq 40\%$ response analysis as one of the key secondary endpoints. It was decided to not include this in the hierarchical testing of secondary endpoints.
- An analysis of the percentage of subjects who achieve a 25% reduction in seizures was added.,
- The Protocol states that the BRIEF rating scale will be used to evaluate cognition in children aged 2-18. The BRIEF-P will be used for children aged 2-4, and the BRIEF will evaluate children aged 5-18. The Protocol further states that the cognition subscale of the BRIEF will be used to evaluate cognition. The BRIEF and the BRIEF-P will be used to evaluate cognition.
- The Protocol states the Clinical Global Impression ratings by Investigator and Caregiver are exploratory endpoints. They are secondary endpoints.
- The protocol states the sample size is approximately 70 randomized subjects. As explained in [Section 6.1.10](#), the sample size was adjusted to approximately 80 randomized subjects based on data from the completed study of Epidiolex in Dravet syndrome.

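### The SAP replaces the protocol's as-treated safety rule with as-randomised, gives no reason and names no exception; its safety time window also needs reconciling

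*SAP*

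**What the plan says.** Protocol 10.2.1 defines the Safety Population as randomised and dosed subjects and gives the grouping rule: "Subjects will be analyzed according to the treatment actually received".

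SAP 5.1.5 keeps the membership ("All safety analyses will be performed on the SAF Population defined as all randomized subjects who receive at least one dose of ZX008 or placebo") but changes the grouping: "Subjects will be analyzed according to the treatment group to which they were randomized".

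SAP 6.9 shows that the change is deliberate. It first restates the protocol ("Protocol states that subjects in the safety population will be summarized by the treatment actually received") and then replaces it: "However, safety data will be presented by randomized treatment group except where noted otherwise". It attaches no reason. SAP 6.4 then applies one grouping throughout: "All safety analyses will be performed for the Safety population (SAF) and will be reported by treatment group, and overall". Neither the subsections of 6.4 nor the tables and listings in SAP Appendix 1 name an output by treatment received.

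Three other places bear on the same tables:

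- SAP 6.4.1.2 reports adverse events for the double-blind treatment period, and SAP 6.1.6 defines that period to include the 14-day taper/transition.
- SAP 6.9 says instead that safety will be summarised only for the combined T+M period.
- Protocol 5.5.7 and SAP 3.2.2 both give ZX008 to placebo-randomised children during transition into the open-label extension.

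**The concern.** Grouping by randomised arm protects an efficacy comparison from selection after randomisation. For safety it works the other way. If a child takes the other arm's product, the effects of that product are credited to the arm that did not supply it, and the contrast between arms shrinks. That is the less cautious direction for a drug which, by Protocol 1.2, was withdrawn globally after reports of heart valve disease and pulmonary hypertension.

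An error is possible. ZX008 and placebo look identical, and within T+M product is dispensed at Visits 3, 5, 6, 8 and 10. Scheduled ZX008 plasma sampling takes place only at Visit 13, in children continuing to the extension. By then every such child is on ZX008, so it cannot reveal an earlier swap. Protocol 8.9 asks for an extra sample after a serious adverse event, but that covers only those children.

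The SAP also leaves no as-treated analysis elsewhere. The protocol grouped the Per Protocol Population by treatment received (10.2.3). SAP 5.1.4 changes that to randomised group as well, and 6.9 does not list that change.

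**Working it through.** The plan states no figure for this effect, so the check is one of text and scale.

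**Inputs.** Allocation is 1:1 (SAP 3.2: "subjects who qualify for the study will be randomized (1:1) in a double-blind manner to receive ZX008"). Protocol 10.1 plans 45 per arm ("a sample size of 45 subjects per treatment group affords 90% power to detect a difference in mean change in seizure frequency from baseline", with SD 58 and a 40-point difference). SAP 6.1.10 plans 40 per arm (SD 55, same difference). The documents give no number of dispensing errors; 1 to 3 is assumed here for illustration.

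**Arm sizes reproduce.** For two-sided 0.05 and 90% power, n = 2(1.960 + 1.282)² × (SD/40)².

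- SD 58: 44.2, rounded up to 45. Power at 45 is 0.905 (normal) or 0.899 (t).
- SD 55: 39.7, rounded up to 40. Power at 40 is 0.902 (normal) or 0.895 (t).

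**One child as a share of an arm.** 1/45 = 2.2%; 1/40 = 2.5%.

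**A single rare event in a placebo-randomised child who took ZX008.**

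| Per arm | As randomised: ZX008 | As randomised: placebo | By treatment received: ZX008 | By treatment received: placebo |
|---|---|---|---|---|
| 45 | 0/45 | 1/45 (2.2%) | 1/46 (2.2%) | 0/44 |
| 40 | 0/40 | 1/40 (2.5%) | 1/41 (2.4%) | 0/39 |

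The only case changes arm.

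**Expected dilution.** Let p_A and p_P be the true event risks on ZX008 and placebo. Suppose m of N placebo-randomised children take ZX008 throughout. The expected difference as randomised is

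p_A − [(N − m)p_P + m p_A]/N = (p_A − p_P)(1 − m/N).

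With m swaps in each direction the factor is 1 − 2m/N.

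- One-way, m = 1 to 3: the difference shrinks by 2.2% to 6.7% of its value (N = 45) or 2.5% to 7.5% (N = 40).
- Two-way, m = 1 to 3: 4.4% to 13.3% (N = 45) or 5.0% to 15.0% (N = 40).
- Example with assumed risks of 10% and 2%, N = 45, m = 1, one-way: 8.0 × 44/45 = 7.8 percentage points.
- m = 0: no change.

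**Transition, where no error is needed.** The SAP 6.1.6 double-blind period is 21 + 84 + 14 = 119 days. For a placebo-randomised child entering the extension, Protocol Table 7 has ZX008 on days 8–14 of transition (7/119 = 5.9% of the period). SAP Table 4 has it on days 1–14 (14/119 = 11.8%). Under 6.1.6 and 6.4.1.2, events on those days count as placebo events. Under the T+M-only statement in 6.9 they are not counted. The two tables also disagree about days 1–7 and must be reconciled.

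**The case against.** The case on the other side has force on several points.

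- **The change is declared.** A reader might infer an oversight or a concealed departure. SAP 6.9 states the old rule, the new rule and an exception clause. What is missing is a reason and any stated exception.
- **The harm is conditional.** A reader might infer that wrong bottles were dispensed. No document reports one. IVR/IWR assigns and logs all medication (Protocol 5.4), bottle numbers are recorded by subject (5.5.2), and returned volumes are checked against the dispensing log and diary (5.8).
- **The cardiac inference goes too far.** A reader might conclude that valve findings on ZX008 would be shown as placebo findings. SAP 6.4.7 sends echocardiogram results to a separate report whose grouping cannot be seen here, and the SAP's table of events of special interest has no cardiac item. Only cardiac events recorded as adverse events pass through the SAP tables.
- **Subject-level traces remain.** Major deviations, daily intake, drug accountability and all adverse events are listed. This does not correct the tables, but the event is not lost.
- **No adverse-event test is affected.** SAP 6.4.1.2 rules out inferential comparison of adverse events. The BRIEF comparison in 6.4.11 is tested in the Safety Population, so the point is not complete.
- **A blanket rule putting any mixed exposure under ZX008 would do harm.** Every placebo-randomised child in transition has mixed exposure by design. Such a rule would carry 105 days of true placebo experience into the ZX008 arm.

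All of this limits the size of the point and shapes the remedy. None of it supplies a reason for leaving the protocol's rule.

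**Conclusion.** The point holds as an unexplained departure from the protocol that costs little to reverse. If a child took the other arm's product during titration or maintenance, the adverse-event, laboratory and vital-sign tables would place that child in the wrong arm. One child is 2.2% to 2.5% of an arm. For common events that is slight; for a rare event it can move the only case from ZX008 to placebo. The dilution percentages rest on an assumed 1 to 3 children taking the wrong product throughout. With no dispensing error, the two rules give identical T+M tables.

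The conflict over the time window does not depend on any error. As the SAP stands, it is unclear whether events in placebo-randomised children on ZX008 in transition enter the placebo column. Its size cannot be given, because the documents do not say how many placebo children enter the extension.

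**What to change.** 1. In SAP 5.1.5, restore the protocol's grouping by treatment received, and delete the corresponding bullet in 6.9.
2. Add a listing of every subject whose received product differed from the assigned one, built from the recorded bottle numbers.
3. If a mixed-exposure rule is wanted, write it to apply only to dispensing errors within T+M, so that placebo children who receive ZX008 by design in transition stay in the placebo group for T+M.
4. Reconcile SAP 6.1.6 and 6.4.1.2 with the T+M-only statement in 6.9, so that placebo-arm events occurring on ZX008 in transition are not counted as placebo events.
5. Reconcile Protocol Table 7 with SAP Table 4 on what the placebo arm receives in days 1–7 of transition.

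Items 1 and 3 need only SAP wording, and item 2 needs one extra listing. Item 4 may change which adverse events appear in the tables, so it should be settled before unblinding. No new data collection is required.

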6. STATISTICAL METHODOLOGY

6.1 STATISTICAL AND ANALYTICAL ISSUES

6.1.1 Statistical Methods

Tabulations will be produced for demographics, baseline, efficacy, and safety parameter. Continuous data will be summarized using descriptive statistics including the number of observations, means, standard deviations, medians, lower and upper quartiles, and ranges. Categorical variables will be summarized showing number of observations, frequencies, and percentages.

This SAP provides summary of statistical methods for comparing the regimens in the double-blind study (cohort 2).

Confidence intervals will be calculated at the 95% confidence level for key parameters or estimates as described in the sections below. Two-sided statistical significance testing (alpha level = 0.05) comparing treatment to placebo will be performed for the primary and secondary endpoints as described in the respective sections below.

All statistical analyses and summaries will be performed using SAS statistical software (Version 9.3 or later version that will be in use at the time of analysis, unless otherwise noted). Adverse events will be coded using the most recent MedDRA version available at the time of analysis and the actual version used will be footnoted in the respective adverse events summary tables. Concomitant medications will be coded using the available recent version of World Health Organization (WHO) Drug dictionary and the version used will be footnoted in the respective medications summary tables.

6.1.2 Multiplicity Strategy and Testing Hierarchy

The multiplicity issues in the statistical inference in this study arise from multiple endpoints.

The efficacy analyses will employ a serial gatekeeper strategy to maintain the Type 1 error rate at $\alpha = 0.05$ across the family of analyses that support the primary and key secondary objectives.

All statistical analyses will be performed and results tabulated with test statistics, p-values, and/or 95% confidence intervals.

Formal statistical testing will be performed for one primary endpoint and two key secondary endpoints for the comparison of ZX008 0.5 mg/kg with Placebo. In order to preserve the overall Type 1 error rate at $\alpha = 0.05$, these tests will proceed as follows:

Step 1: The primary efficacy endpoint (mean convulsive seizure frequency per 28 days) will be formally tested first between the ZX008 0.5 mg/kg and Placebo group. If the comparison is statistically significant at $\alpha = 0.05$ (2-sided) level, the hypothesis testing will proceed to Step 2. Otherwise formal testing of the other hypotheses stops.

Step 2: The secondary efficacy endpoint (proportion of subjects who achieve a $\geq 50\%$ reduction from baseline in convulsive seizure frequency) will be compared between the ZX008 and Placebo

group. If the comparison is statistically significant at $\alpha = 0.05$ (2-sided) level, hypothesis testing will proceed to Step 3. Otherwise formal testing of the other hypotheses stops.

Step 3: The endpoint longest convulsive seizure-free interval endpoint will be compared between ZX008 and Placebo using a significance level of $\alpha = 0.05$ (2-sided).

6.1.3 Subgroups

Select efficacy and safety outputs may be further broken down by the following subgroups:

- Age strata: <6 years, ≥ 6 years

6.1.4 Baseline Definition

The baseline period for Cohort 2 consists of 42 days immediately preceding first administration of study treatment. Any assessment performed during these 42 days before first administration of study treatment will be considered a baseline assessment. Study day 1 will be the first day of study drug administration.

For the analysis of frequency of convulsive seizures endpoints where a baseline convulsive seizure frequency is needed, baseline will include all data from the baseline period of 42 days immediately preceding Day 1 (Visit 3). For all other endpoints, baseline is the last non-missing result prior to first dose from the Baseline period.

6.1.5 Other Definitions

Treatment completers are those subjects that are compliant with IMP at least 85% of dosing days and fulfill at least one of the following criteria:

- Subjects that did not discontinue from the trial prior to end of study visit (Visit 12).
- Cohort 2 Subjects that complete the Treatment Period T+M starting from study Day 1 (Visit 3) through the protocol defined end of study visit (Visit 12).
- Subjects that enroll in the open label extension study.

6.1.6 Visit Windows

The following rules will be used to window data into treatment periods tabulations. For all by-visit tabulations, the nominal visit as recorded on the CRF will be used.

Double Blind Treatment Period	The Double-Blind Treatment Period start date is the date of first dose. The Double-Blind Treatment Period end date is the last date the patient was on study treatment. The Double-Blind Treatment Period includes time from first
-------------------------------	---

	treatment start date, which includes 21 days of Titration period, 12 weeks of Maintenance period and Taper/Transition period (14 days) - For subjects who discontinue early from the study, the double-blind treatment period end date will be the date at the early termination visit (Visit 12).
Titration Period	The Titration Period covers up to the first 21 days of treatment while subjects are titrated to their randomized dose. It begins on the first day of treatment (Study Day 1) and extends through Visit 6 (when the patient has reached their randomization dose). The Titration Period applies to all subjects including placebo recipients. If a subject withdraws from the study prior to treatment in the maintenance period, all safety assessments and events up to and including the date of study withdrawal will be tabulated in the titration period.
Maintenance Period	The Maintenance Period covers the 12 weeks following the end of the titration period. It begins on the date of Visit 6 + 1 day and extends through the end of study/early termination visit (Visit 12).
Titration +Maintenance Period (T+M)	The T+M period combines the Titration and Maintenance periods, beginning on the date of first treatment (Study Day 1) and extending to the end of the 12 week Maintenance Period. The primary efficacy endpoint is calculated based on data from the T+M period.
Taper/Transition Period	The Taper/Transition period consists of approximate 14- days starting from end of study/early termination visit (Visit 12) + 1 day. For patients who are not entering into the open-label extension study, patients will gradually be tapered off of study medication. Patients entering the open-label extension study will first enter the transition phase where all patients will be on a dose of 0.2mg/kg/day at the end of this phase. The end date of this period is considered to be the date recorded at Visit 13.

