6.4.1 Adverse Events

An AE is defined as any unfavorable and unintended sign (including an abnormal, clinically significant laboratory finding), symptom, or disease temporally associated with the use of a medicinal (investigational) product, whether or not considered related to the medicinal (investigational) product. The period of observation for adverse events extends from the time the subject gives informed consent until the end of the titration/transition period (Visit 13). For patients who continue into the open-label extension study, AEs of special interest will continue to be monitored for up to 6 months after the last dose of study medication.

A TEAE is defined as any AE that based on start date information occurs after the first intake of study treatment. All other AEs occurring after enrollment and prior to the first administration of study treatment are defined as non-treatment emergent AEs (non-TEAEs).

Any missing relationship will be considered as “related.”

The severity of AEs (whether non-serious or serious AEs) will be assessed by the investigator as follows:

Severity Definition of Adverse Events:

Mild - A type of AE that is usually transient and may require only minimal treatment or therapeutic intervention. The event does not generally interfere with usual activities of daily living.

Moderate - A type of AE that is usually alleviated with additional specific therapeutic intervention. The event interferes with usual activities of daily living, causing discomfort but poses no significant or permanent risk of harm to the research participant.

Severe - A type of AE that interrupts usual activities of daily living, or significantly affects clinical status, or may require intensive therapeutic intervention.

Any missing severity will be imputed as “severe.”

The original terms used by the investigators in the eCRFs to identify AEs will be coded using the most recent version of the MedDRA implemented by the sponsor at the end of the study.

6.4.1.1 Overview of Events:

The number and percent of patients with at least one of the following events will be summarized in an overall summary table:

- TEAE.
- Serious TEAE
- Related TEAE
- Related serious TEAE.
- TEAE leading to treatment discontinuation
- Death

The percentage denominator for the calculation of percentage will be the number of subjects in the SAF.

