6.4.1.2 Treatment Emergent Adverse Events

The following summaries will display the number and percentage of subjects with adverse events by system organ class (SOC) and preferred term (sorted alphabetically) for each treatment group and overall:

- All TEAEs

- Serious TEAEs
- TEAEs by Maximum Severity
- Study Drug Related TEAEs
- All AEs that lead to premature discontinuation from the study

An additional summary will tally the number and percent of subjects in each treatment group who experience an AE that occurs in at least 5% of subjects. The summary will be presented by preferred term in decreasing order of incidence.

The summaries will be provided for the double-blind treatment period. No inferential statistical methods (i.e., methods that yield p-values) will be used to compare treatment groups on the frequency or severity of AEs.

Additionally, the following listings will be produced for all enrolled subjects:

- All AEs, events considered to be TEAE will be identified in the listing
- Serious AEs
- AEs that lead to premature discontinuation from the study
- Deaths

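### SAP 6.4.1.2 runs the AE tables through Taper/Transition although 6.9 says T+M only, and the exposure summary counts placebo subjects' ZX008 Transition days as placebo

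*SAP*

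**What the plan says.** **AE window.** Of the AE tables by system organ class and preferred term, SAP 6.4.1.2 states: "The summaries will be provided for the double-blind treatment period". SAP 6.1.6 defines that period as one "which includes 21 days of Titration period, 12 weeks of Maintenance period and Taper/Transition period (14 days"). SAP 6.9, which records departures from the protocol, states: "Instead safety will be summarized only for the combined T+M". Protocol 10.5.2 planned safety summaries for Titration, Maintenance and T+M and named no later period.

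**Bounds.** SAP 6.4.1 gives a start but no end: "A TEAE is defined as any AE that based on start date information occurs after the first intake of study treatment". It observes events "until the end of the titration/transition period (Visit 13"). The overview in 6.4.1.1 names no window, and the AE table headers in Appendix 1 name no period.

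**Grouping.** SAP 5.1.5: "Subjects will be analyzed according to the treatment group to which they were randomized". SAP 6.9 repeats that "safety data will be presented by randomized treatment group except where noted otherwise". No exception is noted for adverse events or exposure.

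**Exposure.** SAP 6.2.4.1 reports days on IMP by treatment group over Titration, Maintenance and Taper/Transition combined, as last minus first intake date plus one. There is no split by product. Appendix 1 lists one exposure table, 14.1.5.1b.

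**What placebo subjects take in Transition.** Protocol Table 7 shows placebo on Days 1-7 and ZX008 on Days 8-14. SAP Table 4 shows ZX008 on all 14 days. The SAP introduces its table as hypothetical, but the text below it states the placebo step without that caveat.

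**The concern.** Two programmers following this SAP could produce different AE tables. Under the longer window, the column that serves as the reference for reading the ZX008 safety profile would hold, unlabelled, events that began on ZX008.

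The end of that window also differs between subjects. SAP 6.1.6 closes it at the early termination visit for those who discontinue early but lets it run past Visit 12 for completers. Taper-phase events therefore count for a completer who tapers and not for an early discontinuer who tapers. The Titration row of the same table sets a third bound: for subjects who leave before Maintenance, it collects events up to the date of study withdrawal.

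Exposure is a separate matter. Even if 6.9 settles the AE window, 6.2.4.1 still runs through Taper/Transition. The exposure table would then mix products in the placebo column and cover a different window from the AE tables.

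**Working it through.** **1. Period lengths stated in the plan.**
- T+M: 21 + 12 × 7 = 105 days = 15 weeks, as in SAP 3.2.
- With Taper/Transition: 105 + 14 = 119 days = 17 weeks, as in the protocol synopsis.

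Both figures reproduce. Calling the 17 weeks double-blind agrees with the synopsis. The difficulty lies in using that span as the comparative AE window by randomized group.

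**2. Which AE window do the passages support?**

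| Passage | Window |
|---|---|
| SAP 6.4.1.2 with 6.1.6 | first dose through Taper/Transition |
| SAP 6.9 | T+M |
| Protocol 10.5.2 | Titration, Maintenance, T+M |
| SAP 6.4.10 (C-SSRS behaviour counts), 6.2.4.2 (compliance) | T+M, or Maintenance within it |
| SAP 6.4.1 (TEAE), 6.4.1.1 | no end bound |

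The weight of the text is on T+M. SAP 6.4.1.2 conflicts with it through the period label it borrows from 6.1.6.

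**3. Exposure days by the 6.2.4.1 formula, on nominal visit days.**
- First dose is Day 1 and Visit 12 is Day 106. Transition Day 1 is therefore Day 107, and the last dose under this protocol is at Visit 13, Day 120.
- Extension entrant: 120 − 1 + 1 = 120 days.
- Completer who tapers: last dose on taper Day 8 = Day 114, so 114 days.

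**4. Share per placebo extension entrant.**
- Protocol Table 7: 7/120 = 5.8%.
- SAP Table 4: 14/120 = 11.7%.
- On the 119-day sum of periods: 7/119 = 5.9% and 14/119 = 11.8%.

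**5. Share of the placebo arm's total.** Let g be the fraction entering the extension and z the ZX008 days per entrant. With no dropout, the share is g·z / (g·120 + (1 − g)·114). The documents give no figure for g, so 0.5 to 1.0 is assumed.

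| | g = 0.5 | g = 1.0 |
|---|---|---|
| z = 7 | 3.5/117 = 3.0% | 7/120 = 5.8% |
| z = 14 | 7/117 = 6.0% | 14/120 = 11.7% |

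In subject-days (n·g·z), with n = 40 (SAP 6.1.10) to 45 (Protocol 10.1):
- z = 7: 40 × 0.5 × 7 = 140 to 45 × 1 × 7 = 315.
- z = 14: 40 × 0.5 × 14 = 280 to 45 × 1 × 14 = 630.

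Dropout lowers these totals.

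**6. Unequal end bounds under the longer window.** A completer who tapers contributes 114 − 106 = 8 days (to last dose) to 120 − 106 = 14 days (to Visit 13) after Visit 12. An early discontinuer who tapers contributes none after the early termination visit.

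**The case against.** The best reply is that the matter is already settled. SAP 6.9 exists to say what replaces the protocol's plan, it says T+M only, and Protocol 10.5.2 points the same way. If 6.9 governs, placebo subjects' Transition events stay out of the AE tables and one sentence needs aligning. That stands as a reading of intent, and a claim that nothing resolves the conflict would go too far. It does not correct 6.4.1.2, and it leaves exposure untouched.

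A second reply is that exposure is defined as days on IMP, which covers either product, and that listings of daily IMP intake (16.2.5.1b) and of individual events (16.2.7.1b) are planned. The data will indeed be recoverable by subject. The summary table is still presented by treatment group, and a reader will take the placebo row as time on placebo.

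Third, ending the comparison at T+M takes events during ZX008 taper out of the main tables, whereas splitting off only placebo subjects' Transition data would cure the mixing. That is a fair alternative. It would leave the conflict with 6.9 and the unequal end bounds in place, and separate Taper/Transition tables keep the taper events visible.

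Three stronger inferences are not supported:
- **That the longer window can only raise the placebo AE count, or must hide ZX008 harm.** The ZX008 arm also accrues events in those days. The Titration row in 6.1.6 runs to the date of study withdrawal, and the documents do not say that this coincides with the early termination visit.
- **That every early discontinuer tapers as a completer does.** Protocol 5.5.5 describes a taper for them, but Protocol 4.5 leaves immediate stopping or tapering to the site investigator. The contrast in step 6 applies only to those who taper.
- **That mixed exposure distorts AE rates.** SAP 6.4.1.1 states: "The percentage denominator for the calculation of percentage will be the number of subjects in the SAF". No planned AE percentage uses days of exposure.

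**Conclusion.** The point holds. SAP 6.4.1.2 with 6.1.6 contradicts 6.9. If followed with grouping as randomized, it places ZX008-period events of placebo extension entrants in the placebo column, and its end bounds differ between completers, early discontinuers and those who leave before Maintenance. The size of the effect on AE percentages, and the direction of any change in the difference between arms, cannot be determined from the documents. The comparison is descriptive, since 6.4.1.2 plans no p-values, and no efficacy result is touched.

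The exposure fault does not depend on which AE window is used. It amounts to 5.8% or 11.7% of days per placebo extension entrant, and 3.0-5.8% or 6.0-11.7% for the arm. Those arm figures rest on an assumed 50-100% entry into the extension, no dropout and nominal visit days. The choice between 7 and 14 days is open because the two transition tables disagree. This should be fixed, because the placebo column is the reference for the safety profile, but it does not undermine the trial.

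**What to change.** 1. In SAP 6.4.1, 6.4.1.1 and 6.4.1.2, set the comparative AE window as first dose to end of T+M, in line with 6.9. Apply that bound to the TEAEs that enter the comparative tables, and name the window in the table titles.
2. State one end bound for early discontinuers and make it agree with the Titration row of 6.1.6.
3. In 6.2.4.1, report exposure by treatment group for the same window.
4. Report Taper and Transition events and exposure in separate tables by the product being taken, for completers and for early discontinuers who taper, so that events on taper remain visible.
5. Reconcile SAP Table 4 and its text with Protocol Table 7 on what placebo subjects take on Transition Days 1-7.

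The safety population definition need not change. The cost is SAP wording and one or two additional AE and exposure tables, with no new data collection.
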